9.6 Analysis of Secondary Endpoints

There are four secondary objectives for this study. Descriptive statistics will be used for these objectives.

The first is to assess the value of supine MRI for radiologists performing second look US examinations/ biopsies following identification of new lesions on MRI, and performing preoperative lesion localization using supine MRI guidance. This value will be assessed by both qualitative (survey of radiologists on perceived usefulness of supine MRI for imaging localization/procedures*) and quantitative measures (success rate of second-look ultrasound lesion localizations and procedures utilizing supine MRI guidance). Procedures include lesion biopsy and pre-surgical lesion localization performed by radiologist.

A frequency table will be calculated for the survey questions and the success rate of second-look biopsies and/or localizations.

The second is to assess the perceived benefit of supine MRI for surgical planning as measured by the collective results of a survey of surgeons performing BCT in our study patient population. A frequency table will again be calculated for the survey responses.

The third is to explore the effect of supine MRI on influencing BCS outcomes by determining the percent of patients requiring re-excisions or having pathologic positive margins when supine MR imaging is performed and available for surgical planning purposes. This will be an exploratory endpoint.

The fourth and final secondary endpoint is to assess the perceived value of supine MRI for adjuvant radiation breast treatment planning as measured by the collective results of a survey of radiation oncologists treating patients in our study population post-operatively. Again, a frequency table will be calculated for the survey responses.

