1.1 Study Design and Hypotheses

This study is designed as a prospective Phase II trial aimed to determine the value of supine breast MRI for women newly diagnosed with stage I-III non-inflammatory breast cancer undergoing upfront surgery or neoadjuvant therapy (NAT).

We hypothesize that breast MRI with supine sequences will provide advanced image-based characteristics for (1) radiological procedures (2) surgical operations and (3) adjuvant radiation delivery, and further hypothesize that these images will allow for superior characterization and localization of breast lesions as compared to traditional imaging studies (mammography, ultrasound, prone MRI). This will be measured by a combination of qualitative (clinician surveys of supine MRI usefulness for radiologic and surgical procedures and for radiation treatment/delivery) and quantitative measures (correlation in residual tumor size estimation with the gold standard method, success rate of US-guided lesion identification and/or biopsy performed with supine MRI guidance, and rate of re-excisions for breast conserving surgical operations when supine MRI used for surgical planning).

More specifically, we hypothesize that:

- (1) Supine breast MRI will provide an accurate assessment of residual breast tumor size
- (2) Supine breast MRI will be superior to other imaging modalities in estimation of final tumor size as determined on post-operative pathology (gold standard).
- (3) Supine MRI will help radiologists identify suspected satellite lesions and/or additional suspicious findings during the second look ultrasound procedure. Tissue sampling under sonographic-guidance is more cost effective and patient centric for the patient compared to biopsy under MRI-guidance; therefore, the correlation of MRI findings with ultrasound findings is an important patient-centered endpoint.
- (4) Supine breast MRI will improve surgical planning efforts for breast conserving surgery by providing surgeons with more accurate information regarding the tumor's location within the breast in the supine position, which will translate into reduced re-excision rates associated with this procedure.
- (5) Supine breast MRI will improve adjuvant radiation therapy planning efforts following breast surgery by providing radiation oncologists with more accurate imaging information of the patient in the supine position, allowing for potentially improved radiation delivery

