In the upfront surgery setting, the use of Breast MRI has been shown to compliment traditional

imaging modalities (MMG/US) for determining extent of disease; however there remains a problem with over-estimation of lesion size. This combined with the frequency of identification of second lesions which require biopsy (and are often not visible on MMG/US) has been shown to correlate with increased use of mastectomy, with patients often deferring biopsy altogether. Whether or not supine MRI can improve upon correlation with tumor size in the upfront surgery setting and whether or not supine MRI can lead to improved identification of second lesions requiring biopsy has not been tested.

In the NAT setting, breast MRI has demonstrated higher accuracy over physical examination, mammography, and targeted breast ultrasound in the evaluation of tumor response to NAT and prediction of amount of residual disease. [12, 20-28]. The correlation of residual tumor size following NAT and histopathology in patients who underwent prone MRI before BCS has been reported to be approximately $r=0.7$ (Bhattacharyya et al ($r=0.71$), Rosen et al ($r=0.75$), Martincich et al ($r=0.72$), Segara et al ($r=0.75$)[12, 27-29]. For patients who require NAT for downstaging to BCT, repeating the MRI after NAT (pre-surgery) is standard for surgical treatment planning. In practice, it is uncommon to exclusively rely on a single imaging modality for breast cancer evaluation, and newly diagnosed breast cancer patients routinely have diagnostic mammography and ultrasound imaging as well. In patients undergoing NAT, these images are also repeated after NAT (pre-surgery) for surgical treatment planning.

One of the challenges inherent with the current breast MRI design is that the images are obtained with the patient in the prone position. Tumors are displayed to both radiologists and surgeons in relation to their position in the prone breast, however both ultrasound and surgery are performed on the supine breast. The changes in breast position- especially for patients with large or pliable breasts- can significantly displace breast tumors, making it difficult for radiologists to correlate MRI and sonographic findings, and for surgeons to localize tumors intraoperatively[33, 34].

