3. PARTICIPANT SELECTION

3.1 Inclusion Criteria

- 3.1.1 Participants must be female
- 3.1.2 Participants must have a pre-operative standard mammogram with or without ultrasound. These may be performed at outside institutions but must be reviewed at BWH/DFCI.
- 3.1.3 Participants must have biopsy confirmed and clinical stage I, stage II, or stage III non-inflammatory breast carcinoma. If biopsy was done at an outside hospital, pathology will be reviewed at (BWH, BWFH)
- 3.1.4 Patient must meet standard MRI guidelines and be able and willing to undergo MRI
- 3.1.5 Participants must be candidates for definitive local therapy with breast conserving therapy or deemed as potential candidates following NAT (this takes into account tumor to breast size ratio appropriate for BCT, and the ability to undergo standard radiation therapy post-operatively).
- 3.1.6 Study participants will be restricted to those aged ≥ 18 .
- 3.1.7 Ability to understand and the willingness to sign a written informed consent document.

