Patients deemed candidates for BCS with upfront surgery will proceed to surgery using the supine and prone imaging studies for surgical planning. Patients who will be receiving NAT per their clinical treating team. Post NAT (pre-surgical) imaging will be obtained at the completion of NAT (refer to Section 5.2.2). These imaging studies will then be reviewed by the treating radiologist and surgeon, and will be utilized for surgical planning. Surgery will be either standard BCT or mastectomy (with appropriate nodal intervention including sentinel lymph node biopsy and/or axillary dissection), as deemed appropriate by the treating surgeon. No investigational or commercial agents, or devices will be used or administered during the operation with the intent to treat the participants' breast cancer. When BCT is performed, standard cavity shave margins will be taken (as per institutional guidelines). At the conclusion of the operation, the surgical specimen will be sent for histopathology. If the final pathology indicates that there are positive margins amendable to resection, the patient will be scheduled to undergo re-excision and/or mastectomy in the standard operating room. At the discretion of the treating surgeon, additional re-excisions may be performed for close margins not meeting the definition of a true positive margin. Following completion of each BCT operation, the attending surgeon will be asked to complete a brief survey to assess their perceived usefulness of the supine MRI data in surgical planning/lesion localization.

This protocol will include the standard imaging sequences to image the patient in the prone position and identify the extent of the disease. In addition, a single post-contrast MRI VIBE sequence of the breast with the patient in the supine position will be obtained. The prone and

supine MRI images will be registered in the image-processing software, 3D Slicer, and the segmented tumor models will be overlaid on the images. Screenshots showing the displacement of the tumor from the prone to the supine images will be provided to the surgeon to plan the tumor resection. The supine post-contrast sequences will be used to estimate the tumor position with respect to fixed landmarks such as the nipple, skin and chest wall. If there are additional findings seen initially on MRI, the supine sequence will help to localize the findings during second look ultrasound.

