For patients who received NAT, post-NAT pre-operative breast MRI with supine sequence will be obtained. If tumor was visible pre-NAT on the other imaging modalities such as mammogram, 2D and/or 3D ultrasound they will also be performed at post-NAT. These images will be used to determine if preoperative lesion localization is necessary using either radioactive seed or wire placement; if required, these images will be utilized by the breast imaging service preoperatively for lesion localization procedure per standard practice and the radiologist will be surveyed post-localization regarding usefulness of supine MRI for lesion localization procedure. Supine MRI will be provided in addition to standard imaging modality images for patients ultimately eligible for breast conserving surgery for preoperative surgical planning and for intraoperative tumor resection.

Patients enrolled to participate in this study will receive standard of care with breast conserving therapy or mastectomy for local therapy. Detailed risks and benefits of participating in the study will be reviewed with patients prior to obtaining consent, and all questions will be answered. After general endotracheal anesthesia is induced, the standard operation will be performed by a breast surgical oncologist, including a lumpectomy or mastectomy, with or without sentinel node biopsy and/or possible axillary dissection. The surgical specimen will be sent for standard histopathology. Final specimens will include the original lumpectomy specimen, any nodal tissue (sentinel node(s) versus axillary dissection components if nodal procedure was performed), and shave margins/targeted re-excisions. These samples will be sent for analysis by pathology.

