5.2.2 Post-NAT Evaluation

For patients undergoing NAT, repeat evaluation with imaging studies will be performed at the conclusion of NAT treatment,. Imaging will include dedicated pre-surgical breast MRI in both prone and supine positions, as well as ultrasound and mammography as deemed necessary by the treatment team. Imaging protocols utilized for post-NAT evaluation will be per institutional standards and will be consistent with those utilized for pre-NAT evaluation.

These imaging studies will then be reviewed by the treating radiologist and surgeon, and determination will be made if a radiographic complete response (rCR) has occurred. Quality of the supine MRI sequence will be determined by the attending radiologists, and at this time if the quality is deemed unacceptable for interpretation, the image will not be utilized in residual tumor calculations. If rCR has not occurred, estimated sizes and volumes of the remnant tumor will be made using each imaging modality by the treating radiologist and recorded in standard format. If additional disease is uncovered at this time, it will also be recorded. Using the information obtained from the totality of imaging studies, the surgeon will determine whether or not the patient is eligible to proceed with BCT or mastectomy.

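### The exploratory re-excision and positive-margin rate is tied to breast-conserving operations that are chosen after the MRI is read, and no endpoint shows how many candidates moved to mastectomy

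*Combined protocol and SAP*

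**What the plan says.** - **Endpoint.** Section 9.6, third secondary endpoint, describes its measure of BCS results as "determining the percent of patients requiring re-excisions or having pathologic positive margins when supine MR imaging is performed". It is labelled exploratory, and the secondary objectives are analysed descriptively. No denominator is written.
- **Denominator by implication.** Section 1.1 lists among its quantitative measures the "rate of re-excisions for breast conserving surgical operations when supine MRI used for surgical planning". It describes recording margins and reoperation in its paragraph on patients having breast-conserving therapy (BCT). Section 5.1 provides the supine images "for patients ultimately eligible for breast conserving surgery for preoperative surgical planning".
- **Comparison.** The same paragraph of section 1.1 compares these measures with historical data to judge what supine imaging did to surgical outcomes. Neither the source nor the denominator of those data is given, and 9.6 does not mention the comparison. Hypothesis 4 in section 1.1 predicts fewer re-excisions.
- **Who enters.** Section 3.1.5: "Participants must be candidates for definitive local therapy with breast conserving therapy or deemed as potential candidates following NAT".
- **When the operation is chosen.** For NAT patients, section 5.2.2 says that on all the imaging "the surgeon will determine whether or not the patient is eligible to proceed with BCT or mastectomy". For everyone, section 5.1 says "Surgery will be either standard BCT or mastectomy".
- **Background.** Section 2.1 says that over-estimation of lesion size on breast MRI, combined with second lesions needing biopsy, "has been shown to correlate with increased use of mastectomy, with patients often deferring biopsy altogether".
- **What is not counted.** No objective in 1.2 or 1.3 and no analysis in 9.5 or 9.6 reports mastectomies, changes of surgical plan, or an outcome over all candidates. The surgeon survey follows BCT operations only (5.1, 5.2.3).

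**The concern.** The group in which the rate is measured is formed after the imaging under study and partly by it. A low re-excision rate among the women who still have BCS has two possible explanations. The surgeon may have localized the tumor better, which is hypothesis 4. Or the extensive, margin-prone cases may have left the denominator by going to mastectomy. The planned percentage looks the same either way, and the number of mastectomies that would help to separate the two is not a planned output.

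A single-arm percentage misleads only when it is set against something. Section 1.1 does that with its historical comparison. If the historical rate comes from patients selected for BCS in a different way, the difference mixes selection with localization.

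**Working it through.** The plan gives no rate, number of patients or power for this endpoint, so there is no figure to reproduce. The check asks how far the rate can move when supine MRI has no effect on localization.

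**Inputs.** N = 73 is borrowed from section 9.2, where it is the eligible number for the primary correlation. The rest are assumptions: share of difficult cases q = 0.20, risk of re-excision or positive margin 0.40 in difficult cases (p_d) and 0.15 in the others (p_e), and no true effect. The share of difficult cases moved to mastectomy, s, is varied.

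**Formulas.**
- Mastectomies M = s·q·N; BCS patients B = N − M
- Events E = (1 − s)·q·N·p_d + (1 − q)·N·p_e
- BCS rate = E/B
- Conserved in one operation = (B − E)/N, treating every event as a failure to finish in one operation

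| Difficult cases moved | M | B | E | BCS rate | Conserved in one operation |
|---|---|---|---|---|---|
| None | 0 | 73.0 | 5.84 + 8.76 = 14.60 | 20.0% | 58.40/73 = 80% |
| Half | 7.3 | 65.7 | 2.92 + 8.76 = 11.68 | 17.8% | 54.02/73 = 74% |
| All | 14.6 | 58.4 | 0 + 8.76 = 8.76 | 15.0% | 49.64/73 = 68% |

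The BCS rate improves while fewer women keep the breast in one operation.

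**Other reading of 9.6.** If all patients form the denominator and mastectomies count as non-events, the rates are 11.68/73 = 16.0% and 8.76/73 = 12.0%. The missing denominator therefore does not rescue the endpoint.

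**Conversion unrelated to risk.** Move the same 7.3 patients, 10% of each group: E = 0.9 × 14.60 = 13.14, and 13.14/65.7 = 20.0%. There is no bias.

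**Range.** With d = p_d − p_e, the fall is d·(q/2)·(1 − q)/(1 − q/2) if half the difficult cases move and d·q if all do. Take q from 10% to 30%, p_d from 40% to 50% and p_e from 10% to 15%, so d runs from 0.25 to 0.40.
- Half moved: from 0.25 × 0.05 × 0.90/0.95 = 1.2 points to 0.40 × 0.15 × 0.70/0.85 = 4.9 points.
- All moved: from 0.25 × 0.10 = 2.5 points to 0.40 × 0.30 = 12.0 points.

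**Sampling error for scale.** At 17.8% of 65.7 patients the standard error is √(0.178 × 0.822/65.7) = 4.7 points, larger than the 2.2-point fall in the central case.

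**The case against.** The strongest reply is that this is an exploratory, descriptive secondary endpoint with no test or threshold, and that re-excision and margin rates are naturally reported among lumpectomy patients. Both points stand. They limit the weight of the concern, and the BCS rate should be kept. They do not remove the historical comparison in section 1.1, which is where a selected denominator could mislead.

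Attribution to supine MRI is weak. All patients having supine MRI already have prone MRI (section 6), and the prone study is the one described as showing extent of disease (5.1, 5.2.1). The supine scan is a single sequence used for tumor position. The mastectomy statement in 2.1 concerns existing breast MRI, and the same paragraph says supine MRI is untested in this role. This stands: any shift would belong to the two scans together and, in NAT patients, partly to response to NAT.

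There are also mitigations. MRI-only lesions are to get second-look imaging, with biopsy of suspicious ones (5.2.1), and known BRCA carriers and multicentric disease are excluded (3.2). If the historical patients were also selected for BCS after prone MRI, much of the selection would be common to both groups. The documents do not say whether they were.

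A reader might infer that the planned rate will nearly halve by selection alone. That needs an extreme case: of 60 candidates with 12 destined for re-excision (20%), exactly 6 of those 12 and none of the other 48 move, giving 6/54 = 11.1%. Nothing in the documents supports so precise a selection.

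**Conclusion.** The concern holds as a limit on interpretation. The documents support four facts: entry as candidates or potential candidates, a choice of operation after imaging, a rate framed by breast-conserving operations, and no count of conversions. Under them, the rate can fall with no localization benefit.

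Whether it will, and by how much, cannot be known from the documents. In the assumed central case the fall is 2.2 points (half the difficult cases moved) to 5.0 points (all moved). It is zero if conversion is unrelated to margin risk.

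A reader might also infer that 9.6 explicitly restricts the analysis to BCS patients, that supine MRI is known to increase mastectomy, or that the primary result is compromised. The documents support none of these. The restriction is inferred from section 1.1 and from the BCS framing in 9.6, the mastectomy link is stated for breast MRI in general, and the primary objectives concern tumor size, location and geometry.

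**What to change.** In section 9.6, third endpoint:

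1. State that the re-excision and positive-margin percents use patients who had BCS as denominator.
2. Add two descriptive rows over all BCT candidates at registration, with upfront and NAT patients shown separately because the latter may be only potential candidates at entry: (a) percent with the breast conserved in a single operation; (b) percent with initial or later mastectomy, with the recorded reason.
3. Make the historical comparison of section 1.1 only where both groups have the same denominator.
4. Interpret hypothesis 4 from the BCS rate together with (a) and (b). State that any shift reflects prone plus supine MRI and, in NAT patients, response to NAT, so it cannot be credited to supine MRI alone.

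The rows have no concurrent comparator and so do not establish cause, but they make a shift visible. The cost is one extra case report form field for the reason for mastectomy, two table rows, and a more cautious statement on hypothesis 4. Operation type should already be available, since patients not operated on at the study institutions are removed (section 5.5). No patients, imaging or tests are added, and the primary analysis is unchanged.

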9.7 Reporting and Exclusions

1. Patients who are not evaluable for tumor evaluation by MRI as a result of MRI-related problems (ie degree of contrast washout for supine MRI prevents MRI interpretation as deemed by attending radiologist) will not be included in the primary analysis.

2. Patients who do not have surgical treatment at our institution will not be included in the primary analysis.

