4. REGISTRATION PROCEDURES

4.1 GENERAL GUIDELINES FOR DF/HCC INSTITUTIONS

Institutions will register eligible participants in the Clinical Trials Management System (CTMS) OnCore. Registrations must occur prior to the initiation of protocol therapy. Any participant not registered to the protocol before protocol therapy begins will be considered ineligible and registration will be denied.

An investigator will confirm eligibility criteria and a member of the study team will complete the protocol-specific eligibility checklist.

Following registration, participants may begin protocol therapy. Issues that would cause treatment delays should be discussed with the Overall Principal Investigator (PI). If a participant does not receive protocol therapy following registration, the participant's registration on the study must be canceled. Registration cancellations must be made in OnCore as soon as possible.

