In addition, a single post-contrast MRI VIBE (volumetric interpolated breath-hold examination) sequence of the breast with the patient in the supine position will be obtained. Prior to obtaining this MRI, a second dose of gadolinium MRI contrast agent may be given at the discretion of the radiologist, with dose calculated by the radiologist per institutional policy, to ensure adequacy of supine MRI images. The supine post-contrast sequences will be used to estimate the tumor position with respect to fixed landmarks such as the nipple, skin and chest wall. If MRI identifies additional disease not initially seen on other imaging exams, repeat ultrasound and/or mammogram with additional views will be performed ('second look' exams) to attempt to identify these lesions on an additional imaging modality. Biopsy of newly identified suspicious lesions will be executed with MRI, ultrasound, or stereotactic guidance at the discretion of the treatment team, and histopathologic-radiographic correlation will be performed.

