5.5 Criteria for Taking a Participant Off-Study

If the patient is enrolled in the study, and they are unable to undergo supine MRI for any reason, or during the course of the supine MRI they are unable to complete the supine MRI series, they will discontinue participation in the study at that time. Those patients who, following enrollment in the trial, do not proceed to receive a pre-surgical MRI, or who do not receive surgery at one of our institutions, will be removed from the study.

Participants will also be removed from study when any of the following criteria apply:

- Lost to follow-up
- Withdrawal of consent for data submission
- Death

The reason for taking a participant off study, and the date the participant was removed, must be documented in the case report form (CRF).

For Centralized Subject Registrations, the research team submits a completed Off Treatment/Off Study form to ODQ when a participant comes off study. This form can be found on the ODQ website or obtained from the ODQ registration staff.

For Decentralized Subject Registrations, the research team updates the relevant Off Treatment/Off Study information in OnCore.

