9.5 Analysis of Primary Endpoints

There are three primary objectives of this study, each with unique endpoints.

The first is to evaluate the correlation between prone breast MRI and pathologic measurement in estimating tumor size, and the correlation between supine breast MRI and pathologic results. A 95% confidence interval will also be calculated for each correlation coefficient. One sample z-test will be conducted to compare whether these correlation coefficients are different from 0.6.

The second is to compare the correlation between supine breast MRI and pathologic measurement for estimation of tumor size, and the correlation between existing breast imaging modalities and pathologic tumor size. Similarly, correlation coefficient will be calculated between supine MRI and the pathologic results and between existing breast imaging modalities and the pathologic tumor size. Two-sample z-test for comparing correlated correlation coefficients will be conducted to compare whether these two correlation coefficients are equal.

The third is to characterize the changes occurring in breast tumor-associated properties/ dimensions between the prone and supine imaging position for all patients with pre-surgical MRIs. We will also determine the correlation of tumor location and geometry on pre-NAT and post-NAT (pre-surgical) supine MRI with prone MRI among the subgroup of patients with pre and post NAT imaging. As described in Section 2.1, in our prior work comparing prone to supine MRI, we utilized image processing software that enabled us to generate tumor models and specifically calculate differences in the metrics computed from the segmented tumor label maps on supine and prone MRI. As a first order statistics, we plan to examine differences in the shape

and size of the tumor on supine and prone MRI. Further, we hope to correlate these difference metrics with variables including but not limited to breast size (measured on the axial slice through the nipple) and location (inner/outer, upper/lower). Correlation coefficients will be calculated for parameters related to tumor shape and size between supine and prone MRI, and one sample t-test (or non-parametric Wilcoxon test) will be used to test whether the difference in shape and size parameters between these two measurements are significantly different from 0. A regression model will be used to check whether these differences are correlated to breast size and location, age and other clinical characteristics.

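### Section 9.7 removes the whole patient for an unreadable supine scan, which needlessly drops usable prone-pathology pairs, and no count of failed supine scans is planned beside the supine correlation

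*Combined protocol and SAP*

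**What the plan says.** Section 9.7 item 1 takes out of the primary analysis "Patients who are not evaluable for tumor evaluation by MRI as a result of MRI-related problems". The explanatory parenthesis names one problem, supine contrast washout that stops the attending radiologist from reading the scan. The unit removed is the patient, with no split by modality or objective.

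Section 5.2.2 covers the evaluation after neoadjuvant therapy (NAT) and works at a different level: "if the quality is deemed unacceptable for interpretation, the image will not be utilized in residual tumor calculations". No matching image-level rule is written for patients going straight to surgery.

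Section 9.5 makes prone-pathology and supine-pathology two separate correlations under the first primary objective. Of these it says "A 95% confidence interval will also be calculated for each correlation coefficient" and "One sample z-test will be conducted to compare whether these correlation coefficients are different from 0.6". Section 9.1 names the prone-pathology correlation as the measure for the primary objective.

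On scans that are not finished, section 5.5 says of patients that if "they are unable to complete the supine MRI series, they will discontinue participation in the study at that time". It also requires the off-study reason and date to be entered in the CRF. Sections 9.1 to 9.7 plan no tabulation of supine scans that were not completed or could not be read.

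**The concern.** A patient can have a good prone MRI, a pathology size and a washed-out supine scan. The prone-pathology correlation needs only the first two, yet 9.7 as worded removes that patient from it. Section 5.2.2 would keep the patient. Two analysts could therefore build two different prone-pathology sets from the same protocol, and the choice should not be left until the data are in.

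The second part matters more. The study sets out to judge the value of adding a supine sequence. Its supine correlations can be computed only where that sequence was readable. The protocol expects some trouble with image quality: 9.7 names washout, and section 5.2.1 allows a second contrast dose "to ensure adequacy of supine MRI images". A supine r without the proportion of failed scans beside it does not tell the reader how often the sequence yields a usable size.

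**Working it through.** **Which analyses the two rules affect**

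| Analysis in section 9.5 | Scans needed | 9.7 (patient out) versus 5.2.2 (image out) |
|---|---|---|
| Supine-pathology | supine | same set |
| Supine versus standard imaging | supine and comparator | same set |
| Prone-to-supine change | both MRIs | same set |
| Prone-pathology | prone only | **9.7 drops usable pairs** |

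**Inputs.** Section 9.2 gives 73 eligible patients, r = 0.85 against 0.70, two-sided alpha 0.05, 90% power, 10% dropout and 80 accrued. (Section 1.1 gives 74 recruited, a separate discrepancy; section 9.2 is used here.) Section 9.5 gives a null of 0.6. Section 2.1 gives a prone r of about 0.7 after NAT. The documents give no supine failure rate, so 5%, 10% and 15% are assumed.

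**The plan's own figure.** With Fisher's z, power = Φ[(atanh 0.85 − atanh r0)·√(n − 3) − 1.96]. Here atanh 0.85 = 1.2562, atanh 0.70 = 0.8673 and atanh 0.60 = 0.6931. At n = 73 and r0 = 0.70: 0.3889 × √70 = 3.253, and Φ(3.253 − 1.96) = 90.2%. The stated 90% reproduces.

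**Patient-level exclusion in the prone-pathology analysis.** After 10% dropout, 80 × 0.90 = 72. If failures come on top of dropout and each affected patient has a readable prone scan and pathology, then n = 72 × 0.95, 0.90 or 0.85 = 68.4, 64.8 or 61.2, rounded below. The interval is tanh(atanh 0.70 ± 1.96/√(n − 3)).

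| Assumed failure rate | n | Power, 0.85 vs 0.70 | Power, 0.85 vs 0.60 | 95% CI at r = 0.70 |
|---|---|---|---|---|
| 0% | 72 | 89.8% | 99.7% | 0.559–0.802 |
| 5% | 68 | 88.0% | 99.5% | 0.554–0.804 |
| 10% | 65 | 86.5% | 99.3% | 0.550–0.806 |
| 15% | 61 | 84.2% | 99.0% | 0.544–0.809 |

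If unreadable scans are already part of the 10% dropout, n stays at 72 and power at 89.8%.

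**What the unreported proportion would show.** Here the denominator is all 80 accrued, because a pre-surgical supine scan is planned for everyone; the table above starts from 72. Exact (Clopper-Pearson) 95% intervals:

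- 4/80 = 5%: 1.4% to 12.3%
- 8/80 = 10%: 4.4% to 18.8%
- 12/80 = 15%: 8.0% to 24.7%

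These counts are illustrations. The trial is large enough to place the failure rate within a useful range.

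**The case against.** **A single common set is defensible.** The second and third primary objectives compare modalities within patients, and one set keeps the coefficients comparable. This stands for those comparisons, and the fix keeps it. It gives no reason to drop usable pairs from a correlation that is estimated and tested alone.

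**The precision loss is minor and may be nil.** This stands. Section 9.2 does not define dropout, and patients removed under 9.7 could belong to it. If the true prone r is about 0.70, power against the 0.6 null is about 30% at n = 72 and 28% at n = 65, so the exclusion rule hardly affects that test either.

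**The failure count will exist anyway.** Off-study reasons go in the CRF, and 9.7 cannot be applied unless the radiologist judges readability. This also stands: the data should be recoverable. The CRF itself is not in the documents, so one cannot say that it lacks a field for unreadable scans. What is absent is a plan to report the count.

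A reader might go further on three points, and the documents do not support any of them:

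- *That section 5.5 also discards prone-pathology pairs.* When a pre-surgical supine series is not completed, surgery has not taken place and there is no pathology, so no existing pair is thrown away. Following such patients further would extend the design.
- *That patients who never have the scan vanish from the denominator*, because section 4.1 says that, without protocol therapy, "registration on the study must be canceled". This is speculative. Section 5.5 deals specifically with patients who cannot undergo supine MRI and requires a documented reason. Cancellations are themselves entered in OnCore.
- *That leaving out unreadable scans flatters the supine correlation.* Failure could be related to tumor or patient features, but nothing in the documents shows in which direction r would move.

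**Conclusion.** The point holds with limited scope. Section 9.7 conflicts with 5.2.2 on the unit of exclusion, and the practical effect is confined to the prone-pathology correlation. The cost there is small: about 3 percentage points of power at an assumed 10% failure rate (89.8% to 86.5%), about 6 at 15% (to 84.2%), and none if failures are within the 10% dropout. These figures rest on assumed failure rates and on a readable prone scan and pathology in every affected patient.

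The main cost is to interpretation. The supine correlations will describe readable scans only, and the plan calls for no failure proportion beside them. No primary test is invalidated and no bias is demonstrated. The change should still be made, because it settles the analysis set in advance and gives the supine result its context at little expense.

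**What to change.** 1. **Exclude by image.** Reword 9.7 item 1 so that an unreadable scan removes only the analyses that use it, consistent with 5.2.2, for upfront-surgery and post-NAT scans alike. Compute prone-pathology r in all patients with a readable prone MRI and pathology. Keep the common paired set for the supine-versus-standard and prone-versus-supine comparisons, and show prone r on that set too, so that the coefficients can be compared directly.
2. **Report failures.** Beside the primary result, give the number, reasons and proportion (exact 95% CI) of planned pre-surgical supine scans that were not completed or not readable. The denominator is all registered patients in whom the scan was planned. The sources are the off-study reasons already required in the CRF and the radiologist's readability judgement that 9.7 already depends on.

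The cost is a few sentences in section 9 and one short table. The headline may look slightly less favourable with the failure proportion next to it. Amending 5.5 to go on collecting data after an uncompleted scan is optional, would need consent text, and is not part of this correction.
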